5.4 PK Population

The PK population for evaluation of C_{p2hr} and C_{trough} will include all randomized patients who received at least 1 dose of study drug during the double-blind Treatment Period and had at least 1 sample collected.

5.5 Safety Population

The Safety population is defined as those randomized patients who take at least 1 dose of study drug during the double-blind Treatment Period. Safety patients are analyzed according to their actual treatment received on Study Day 1.

6. Data Handling

6.1 Time Points and Visit Windows

Day 1, defined as the Baseline/Randomization visit, is also the first day that study treatment during the double-blind Treatment Period is planned to be started. Should study treatment start at a later date, Day 1 will be defined as the date that

CONFIDENTIAL

study treatment during the double-blind Treatment Period is initiated. Relative days after Day 1 are calculated as (assessment date – Day 1 date) + 1. Relative days prior to Day 1 are calculated as (assessment date – Day 1 date). The day prior to Day 1 is Day -1; there is no Day 0.

6.1.1 Primary efficacy, secondary efficacy, and other efficacy endpoints based on daily pain diary data

The following time point windows defined in [Table 1.1](#) will be used for the analyses of the primary efficacy endpoint, the secondary efficacy endpoints, and other efficacy endpoints based on the ADPS as well as for the secondary endpoint on pain interfering with sleep.

Table 1.1 Definition of time point windows for analyses based on ADPS and sleep interference rated each evening

Time point	Time point window ^a
Baseline	Day -7 to Day -1
Week 1	Days 1 to 7
Week 2	Days 8 to 14
Week 3	Days 15 to 21
Week 4	Days 22 to 28
Week 5	Days 29 to 35
Week 6	Days 36 to 42
Week 7	Days 43 to 49
Week 8	Days 50 to 56
Week 9	Days 57 to 63
Week 10	Days 64 to 70
Week 11	Days 71 to 77

^a relative to the date of first dose of study drug during the double-blind Treatment Period/ date of Randomization/date of Baseline Visit (Day 1)

The Baseline value for ADPS based on Question 5 of the ZBPI will be calculated as the mean value of the corresponding question over Week 2 of the single-blind Run-in Period, provided that ≥5 days with non-missing data from that period are available for analysis. The Baseline value for the interference with sleep using Question 9F of the ZBPI is defined as the value collected at the time of the clinic visit on Day 1 but prior to intake of the first dose of study drug. As a sensitivity analysis, the mean value of Question 9F of the ZBPI of daily diary over Week 2 of the single-blind Run-in Period will be used as the Baseline, provided that ≥5 days with non-missing data from that period are available for analysis.

The post-Baseline values will be calculated as the mean value of the corresponding question, ie, Question 5 for ADPS and Question 9F for interference with sleep of the ZBPI, rated by patients each evening in the daily pain diary and collected during the target week period. A minimum of 4 non-missing data points within the target week period is required for the calculation of the mean value for that particular week.

6.1.2 Secondary efficacy and other efficacy endpoints based on data collected at clinic visits

The rest of the efficacy endpoints based on data collected at clinic visits will follow the visit windows defined in [Table 1.2](#).

Table 1.2 Definition of visit windows for efficacy data collected at each visit

Visit	Target Day of Visit ^a	Acceptable visit window
Screening	Day -28	NA
Run-in ^b	Day -14	NA
Baseline	Day 1	Day 1
Week 2	Day 15	Days 2 to 22 (Day 15-13 days, Day 15+7 days)
Week 4	Day 29	Days 23 to 36 (Day 29-6 days, Day 29+7 days)
Week 6	Day 43	Days 37 to 60 (Day 43-6 days, Day 43+17 days)
Week 11	Day 78	Day 61 to 40 days after the last treatment dose during the double-blind Treatment Period (\geq Day 78-17 days, last treatment dose + 40 days)

^a relative to the date of first dose of study drug during the double-blind Treatment Period/ date of Randomization/date of Baseline Visit (Day 1)

^b weight is collected

In general, the Baseline value for a variable is defined as the last value collected or taken on or before Day 1 and prior to the first dose of double-blind study drug. In cases where there are multiple such values, the non-missing value closest to the start of study treatment is selected. If time is available for an assessment on Day 1, it will be compared with dosing time on Day 1 to define the Baseline value.

Multiple visits within the same window will be dealt with as follows:

- If both scheduled and unscheduled visits fall within the same visit window, the scheduled visit will be used for analysis.
- If multiple scheduled visits occur within a single visit window, then the visit closest to the target day of the visit window will be used in the analysis. If there is a tie, the later visit will be used in the analysis.
- If multiple unscheduled visits occur within a single visit window (with no scheduled visit within the window) then the unscheduled visit closest to the target day of the visit window will be used in the analysis. If there is a tie, the later unscheduled visit will be used in the analysis.

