9.1.1.1 Special Considerations for Bladder Dysfunction-related Adverse Events

In studies with LX9211 in dogs, changes to the urinary bladder (including minimal inflammation, slight urothelial hyperplasia, minimal focal ulceration, and minimal muscle degeneration) were noted. The doses used in these animal studies were much higher than what will be used in this Phase 2. In the Phase 1 SAD and MAD studies with LX9211, no clinically significant CMP, UA findings, or bladder dysfunction-related AEs were reported in any subject.

In this study, bladder dysfunction-related AEs will be closely monitored on an ongoing basis. In addition, an unscheduled visit may be conducted in case of a reported AE suspicious for urinary bladder abnormalities, where additional labs and follow-up may be obtained, as deemed necessary.

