10.4.5.6 Electrocardiogram (ECG)

The actual values of the 12-lead ECG parameters at Baseline, at each time point, and change from Baseline will be summarized using descriptive statistics. The number and percentage of patients with ≥ 1 postBaseline abnormal ECG result will be summarized using descriptive statistics and presented by treatment group.

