6.1.3 Safety analyses

Safety analyses for the laboratory assessments, vital signs, ECG and physical exam data will use the study visit window rules used to assign observations to visits as defined above in [Table 1.2](#).

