7.7.3 Laboratory Evaluations

Data for the following hematology, serum chemistry, lipid panel, and urinalysis analytes received from central laboratory will be listed and summarized by treatment group and visit. If data for any additional analytes are also received, then these will be listed only.

Hematology	Serum Chemistry	Urinalysis
Complete blood count (CBC) with differential Platelet count	Albumin Alkaline phosphatase Alanine transaminase (ALT) Amylase Aspartate transaminase (AST) Total bilirubin Glucose Blood urea nitrogen (BUN) Calcium Carbon dioxide Chloride Creatinine Magnesium Phosphorus Potassium Sodium Total protein Uric acid	Appearance Color Glucose Ketones Nitrite pH Protein Specific gravity Occult blood Leukocyte esterase Bilirubin Urobilinogen Urine microscopy White blood cell Red blood cell Epithelial cells Bacteria Casts Crystals
Lipid panel	Other Samples	
High-density lipoprotein (HDL) Low-density lipoprotein (LDL) Total cholesterol Triglycerides Creatinine phosphokinase (CPK)	Pregnancy tests (females only) Urine screen (drugs of abuse and THC)	

All laboratory data will be reported in International System of Units and conventional units. Out-of-reference-range values will be flagged as high (H) or low (L) in the listings.

For analysis purposes, values preceded by a "<" or a ">" sign (ie, those below or above the limits of quantification) will be considered equal to the lower or upper limit of quantification, respectively.

Laboratory data will be summarized by visit using standard descriptive statistics by treatment group and overall for the Safety population. Changes from Baseline will also be summarized.

For hematology and serum chemistry, shift tables presenting movement in and out of reference range from Baseline to each scheduled post-Baseline visit will be provided by treatment group and overall for the Safety population. Percentages will be based on the number of patients with both non-missing Baseline and relevant post-Baseline results.

For each laboratory analyte, the Baseline value will be defined as last scheduled or unscheduled value collected prior to the first dose of study drug during the double-blind Treatment Period. Assessments carried out on the day of first study drug administration are considered to have taken place before the study drug administration, if the corresponding times have not been recorded.

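### Unscheduled chemistry, urinalysis and vital-sign values drop out of the by-visit safety tables and no any-time summary recovers them; separately, the SAP omits the protocol's abnormal-ECG count

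*SAP*

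**What the plan says.** SAP 6.1.2 gives contiguous visit windows in Table 1.2 and then rules for several visits in one window. The first is "If both scheduled and unscheduled visits fall within the same visit window, the scheduled visit will be used for analysis". An unscheduled visit is used only where no scheduled visit competes: "If multiple unscheduled visits occur within a single visit window (with no scheduled visit within the window) then the unscheduled visit closest to the target" is the one analysed.

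SAP 6.1.3 extends this to safety: "Safety analyses for the laboratory assessments, vital signs, ECG and physical exam data will use the study visit window rules" of Table 1.2.

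The safety tables are built by visit. SAP 7.7.3 summarises laboratory data by visit and plans, for hematology and serum chemistry only, "shift tables presenting movement in and out of reference range from Baseline to each scheduled post-Baseline visit". SAP 7.7.4 and 7.7.5 give by-visit summaries and shifts for vital signs and ECG. None of these sections plans a worst-value or any-post-Baseline table. Baseline, by contrast, may be a scheduled or an unscheduled value (SAP 7.7.3 to 7.7.5).

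The protocol expects unscheduled data. Section 8.1.3 provides for retests as often as clinically needed, Section 9.5 for repeating medically significant abnormal results, and Section 9.1.1.1 says that "an unscheduled visit may be conducted in case of a reported AE suspicious for urinary bladder abnormalities", with additional laboratory tests.

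For ECG, Protocol 10.4.5.6 commits to a patient-level count that is not tied to a visit: the number and percentage with at least one "postBaseline abnormal ECG result will be summarized using descriptive statistics". SAP 7.7.5 has no such count, and SAP Section 8 (Changes in Planned Analysis) does not mention its removal.

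**The concern.** Many unscheduled samples are taken because something looked wrong. If a routine visit in the same window always replaces them, an abnormality that arose and resolved between visits can be missing from every laboratory and vital-sign table although it was measured. The first window is the widest before Week 6: it runs from Day 2 to Day 22, so a reading a few days after the loading dose competes with a visit targeted at Day 15. The protocol's own Phase 1 summary (Section 3.4) describes short-lived events, including one case of orthostatic tachycardia at 300 mg that began 1 hour after dosing and lasted 8 days.

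At stake is the descriptive safety profile of a Phase 2 trial in which urinary bladder findings in dogs led the protocol to ask for close monitoring. No error rate, power figure or efficacy result is affected.

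**Working it through.** **1. Windows (SAP Table 1.2).** Target day minus and plus the stated offsets:
- Week 2: 15 - 13 = 2, 15 + 7 = 22
- Week 4: 29 - 6 = 23, 29 + 7 = 36
- Week 6: 43 - 6 = 37, 43 + 17 = 60
- Week 11: 78 - 17 = 61, up to the last double-blind dose + 40 days

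These reproduce the printed limits. Each day from Day 2 to the end falls in exactly one window.

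**2. What is scheduled (Protocol Appendix A).** Chemistry, urinalysis and seated vital signs: Weeks 2, 4, 6 and 11. ECG and hematology: Weeks 6 and 11 only.

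**3. Days on which an unscheduled value meets a scheduled assessment of the same type.** Assume a patient who attends all visits, with last dose on Day 42. The last window then ends on Day 42 + 40 = 82, giving 82 - 2 + 1 = 81 post-Baseline days, of which 41 (Days 2-42) are on treatment.

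| Assessment | All post-Baseline days | On treatment |
|---|---|---|
| Chemistry, urinalysis, vital signs | 81/81 = 100% | 41/41 = 100% |
| ECG, hematology (Days 37-82) | 46/81 = 57% | 6/41 = 15% |

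With last dose on Day 43 to 46, the first row stays at 100% and the second becomes 57-59% overall and 17-22% on treatment.

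**4. Two readings for ECG and hematology on Days 2-36** (35 of the 41 on-treatment days, 85%). Applied per visit, the Week 2 or Week 4 visit displaces an unscheduled tracing or blood count although that visit has no result of its own to offer. Applied per assessment, nothing displaces it and it is kept. The SAP does not choose.

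**5. How much the scheduled visits would miss.** The documents give no duration of abnormality and no number of unscheduled samples. Assume onset uniform on Days 2-42 (41 onset days), visits on their target days (15, 29, 43), and an abnormality lasting *d* days. A visit on day *v* catches onsets from *v* - *d* + 1 to *v*, restricted to Days 2-42.

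| *d* | Caught at Days 15 + 29 + 43 | Missed by scheduled chemistry/urinalysis |
|---|---|---|
| 3 days | 3 + 3 + 2 = 8/41 | 33/41 = 80% |
| 7 days | 7 + 7 + 6 = 20/41 | 21/41 = 51% |
| 14 days | 14 + 14 + 13 = 41/41 | 0% |

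For the Day 43 ECG alone, the share caught is 2/41 = 5%, 6/41 = 15% and 13/41 = 32%. The missed shares are abnormalities that only an unscheduled visit could show. They do not say how many would actually be sampled.

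**6. ECG count.** Protocol 10.4.5.6 counts patients with any abnormal tracing after Baseline. SAP 7.7.5 counts patients per category at each visit. By-visit counts cannot be added to give a patient-level count, because one patient may be abnormal at both Week 6 and Week 11.

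**The case against.** Several points on the other side are sound.

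- **The values do not vanish.** Protocol 8.1.3 and 9.1.1 send clinically significant laboratory results to the adverse-event record, and so to the treatment-emergent tables. The bladder visit of Section 9.1.1.1 is itself triggered by a reported adverse event. SAP 7.1 lists all collected data, and SAP 7.7.3 flags out-of-range results. A reader might infer that for-cause values are absent from all safety tables; the documents do not support that. What remains is that the adverse-event route depends on the investigator's judgement and carries no values, and that listings give no rates by arm.
- **The rule may not reach safety data in full.** The text reads "Safety analyses for the laboratory assessments, vital signs, ECG and physical exam data will use the study visit window rules used to assign observations to" a visit and cites Table 1.2, while the tie-break rules stand below that table under an efficacy heading. Importing them is the likely reading, since no other rule for choosing among visits is given, but it is not explicit. The reference to observations also lends some support to the per-assessment reading.
- **Some unscheduled values are kept.** With last dose and withdrawal visit on Day 10 and follow-up 35 days later on Day 45, the Week 4 window holds no scheduled visit unless the patient attends one, so an unscheduled value there is used.
- **The direction of bias is not shown.** If the abnormal value came from a scheduled visit, the rule keeps it and drops the later, perhaps normal, retest. Nor do the documents show that one arm would be affected more.
- **The ECG count is not distorted by the window rule.** It is simply not planned in the SAP, which is a separate omission.
- **By-visit tables are what the protocol promises** for laboratory data and vital signs (Sections 10.4.5.3 and 10.4.5.4), and preferring scheduled values there avoids outcome-driven sampling. That is a good reason to keep the rule for those tables, but no reason to have no other summary.

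**Conclusion.** The point holds in a limited form. For chemistry, urinalysis and vital signs, in patients who attend their visits and if the multiple-visit rules apply to safety data as 6.1.3 suggests, every unscheduled post-Baseline value is left out of the by-visit summaries and of any shift table, and no other planned table recovers it. For ECG and hematology on Days 2-36, the SAP is unclear rather than demonstrably wrong.

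The share of abnormalities that could be seen only at an unscheduled visit should be given as a range: 80% to 0% for chemistry and urinalysis as the assumed duration goes from 3 to 14 days. No single figure in that range is supported by the documents.

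Independently of the window rule, the SAP drops a patient-level ECG summary that the protocol promises, without saying so in Section 8. Neither defect threatens the primary analysis. Both are worth correcting because the safety review is descriptive and the repair is small.

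**What to change.** 1. In SAP 6.1.3, state that the multiple-visit rules apply to safety data, only for by-visit tables, and per parameter: if the scheduled visit has no result for a parameter, the unscheduled value in that window is used.
2. Add one row, labelled as worst post-Baseline value from scheduled or unscheduled assessments, to the hematology, chemistry, vital-sign and ECG shift tables. Urinalysis has no shift table, so add a summary of patients with any abnormal post-Baseline result, on the same basis.
3. Restore to SAP 7.7.5 the count of patients with at least one abnormal post-Baseline ECG, including unscheduled tracings. If it was left out on purpose, declare this in Section 8.

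The cost is a few sentences of SAP text, one row per shift table, one urinalysis summary and one ECG count. No new data are needed, and sample size and error rates do not change. The drawback is that for-cause sampling is unevenly timed and more frequent in some patients than in others, so the added rows must be labelled as including unscheduled assessments and read beside the by-visit tables.

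### The visit-window rule gives the early-withdrawal visit no row of its own, so for parameters also taken at Weeks 2 and 4 its values can drop out of the by-visit safety tables and the clinic-ZBPI model

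*SAP*

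**What the plan says.** In the schedule of events (Protocol Appendix A, SAP Appendix 2) the EW assessment shares the Visit 6 column with Week 6. SAP Table 1.2 has rows for Weeks 2, 4, 6 and 11 but none for EW, so study day alone decides where an EW visit is filed.

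SAP 6.1.2 then keeps one visit per window:

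- Scheduled against unscheduled: "If both scheduled and unscheduled visits fall within the same visit window, the scheduled visit will be used for analysis".
- Several scheduled visits: "then the visit closest to the target day of the visit window will be used in the analysis". A tie goes to the later visit.

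SAP 6.1.3 says that laboratory, vital-sign, ECG and physical-exam analyses "will use the study visit window rules used to assign observations to visits as defined above" in Table 1.2. The outputs are organised the same way. SAP 7.7.3 plans by-visit laboratory summaries and, for hematology and serum chemistry, "shift tables presenting movement in and out of reference range from Baseline to each scheduled post-Baseline visit". SAP 7.7.4 and 7.7.5 plan by-visit summaries and shifts for vital signs and ECG. None of these sections has an end-of-treatment row or a worst post-Baseline row. SAP 7.6.2.4 and 7.6.5.2 fit the clinic-ZBPI repeated-measures models by visit.

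**The concern.** An EW visit records the patient's condition on stopping. Suppose the Week 2 visit is on Day 15 and the patient withdraws with an EW visit on Day 20. Both fall in the Week 2 window, Day 15 is nearer the target, and the Day 20 chemistry, urinalysis, vital signs and ZBPI scores enter no by-visit table or model. Calling the EW visit unscheduled gives the same result, because the scheduled visit then wins.

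Stopping-visit values are more likely than routine ones to be abnormal. Urinalysis is among the affected panels, and Protocol 9.1.1.1 asks for close monitoring of bladder-related events. For clinic ZBPI, the lost score is the last one before dropout, on which a missing-at-random model (SAP 6.2.1) leans.

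**Working it through.** **Inputs.** Windows, targets and selection rules come from SAP 6.1.2, and the ±3-day tolerance for Weeks 2 and 4 from the schedule of events. Assumptions: the EW visit can fall on any of Days 2-42 (42 − 2 + 1 = 41 days); routine visits due before it were attended; it counts as scheduled; there is no later Week 6 return.

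**1. Reproduce Table 1.2.**

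- Week 2, "Days 2 to 22 (Day 15-13 days, Day 15+7 days": 15 − 13 = 2 and 15 + 7 = 22.
- Week 4, "Days 23 to 36 (Day 29-6 days, Day 29+7 days": 29 − 6 = 23 and 29 + 7 = 36.
- Week 6, "Days 37 to 60 (Day 43-6 days, Day 43+17 days": 43 − 6 = 37 and 43 + 17 = 60.

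All agree with the stated limits.

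**2. Routine visits on target (Days 15 and 29).**

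| EW day | Competing visit | Result |
|---|---|---|
| 2-14 | none yet | kept, as Week 2 |
| 16-22 | Day 15 | dropped, 7 days |
| 23-28 | none in window | kept, as Week 4 |
| 30-36 | Day 29 | dropped, 7 days |
| 37-42 | none without a return | kept, as Week 6 |

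On Days 15 and 29 themselves there is no second record. Dropped: 7 + 7 = 14 days, and 14/41 = 34.1%.

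**3. Routine visits anywhere within ±3 days.** If the routine visit is k days from target, a later EW visit is dropped when it is more than |k| days past target. Both windows end 7 days past target, so each loses 7 − |k| days. For k = −3 to +3 that is 4, 5, 6, 7, 6, 5, 4 (sum 37, mean 37/7 = 5.29). Over both windows:

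- minimum 4 + 4 = 8 days, 8/41 = 19.5%
- maximum 7 + 7 = 14 days, 34.1%
- mean 2 × 37/7 = 10.6 days, 25.8%

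**4. Sensitivity to the assumptions.**

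- EW visit counted as unscheduled: every EW day after the routine visit in its window is lost, 7 − k days per window. That gives 8 to 20 days over both windows (mean 14). With on-time visits it is the same 14.
- On-time visits plus a return on Day 43: EW Days 37-42 also lose, so 14 + 6 = 20 and 20/41 = 48.8%.
- Stopping days ended at Day 39, before the Week 6 visit tolerance opens: 14/38 = 36.8%.

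**5. Which parameters compete (schedule of events).**

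| Parameter | At Weeks 2 and 4 | At Week 6/EW | EW value can be displaced there |
|---|---|---|---|
| Serum chemistry, urinalysis, seated vital signs, weight, clinic ZBPI | yes | yes | yes |
| ECG, hematology, NPSI, PGIC | no | yes | only if the whole visit is dropped |

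The SAP does not say whether selection within a window is by visit or by parameter.

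**6. A related effect, not counted above.** For EW on Days 16-22, the follow-up visit 35 days later falls on Days 51-57, inside the Week 6 window. Without a Day 43 return, the stopping value is dropped while a value taken about five weeks later is analysed as Week 6.

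**The case against.** The strongest reply is that the important values reach the report by other routes. Protocol 9.1.1 makes a treatment-emergent laboratory abnormality an adverse event if it leads to stopping, needs treatment or is judged clinically significant. The adverse-event tables do not use Table 1.2. SAP 7.1 lists all collected data, and SAP 7.7.3 flags out-of-range laboratory values. This stands, and it limits the loss to by-visit summaries, shift cells and the clinic-ZBPI model. It does not put the values back in those outputs, and it does not cover an abnormal value that met no reporting criterion.

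The efficacy effect is also small. The primary endpoint and the diary-based sleep endpoint use the weekly windows of Table 1.1. Clinic ZBPI 9A-G is secondary, unadjusted and exploratory (SAP 7.6). With on-time visits the model still holds a score from the same window at most 22 − 15 = 7 days before the EW visit.

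Finally, nearest-to-target selection is prespecified and treats all patients alike. A reader might infer that the EW record should always override the routine one for ZBPI 9A-G. That is a trade-off rather than a correction: a Day 22 score would be filed as Week 2 for a patient who drops out, while completers keep a score near Day 15, so assessment timing would depend on dropout status.

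**Conclusion.** The gap is real and minor. For serum chemistry, urinalysis, seated vital signs, weight and clinic ZBPI, the rule leaves out the EW visit on 8 to 14 of 41 possible stopping days (about 20-34%), under the assumptions listed in the working.

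Three stronger readings go beyond the documents:

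- *Stopping-visit safety values reach no table.* ECG and hematology have no competing value at Weeks 2 and 4, and qualifying laboratory abnormalities reach the adverse-event tables.
- *A definite number of patients is affected.* The planned 15% dropout of 74 is 11.1 patients; multiplying by 8/41 and 14/41 gives 2.2 to 3.8. This needs every dropout to attend an EW visit on evenly spread days. Protocol 6.3 only encourages completion of those assessments, patients lost to follow-up have no such visit, and a patient who stops at a routine visit has no second record. The documents give no distribution of stopping days.
- *LX9211 is made to look safer.* That requires more stopping on LX9211 than on placebo, which the documents do not establish.

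**What to change.** In the SAP:

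1. Add an end-of-treatment analysis row (the Week 6 or EOT/EW assessment, wherever it falls) to the laboratory, vital-sign and ECG summaries and shift tables. In those tables the stopping days lost fall from 14 of 41, with on-time visits, to 0.
2. Add a shift from Baseline to the worst on-treatment post-Baseline value, using scheduled, unscheduled and EW results, and define the on-treatment cut-off.
3. State in 6.1.2 and 6.1.3 that selection within a window is by parameter, so that an EW ECG or hematology result is not discarded with its visit.
4. As a separate protocol-SAP mismatch, restore in SAP 7.7.5 the count in Protocol 10.4.5.6, where the number of patients with at least one "postBaseline abnormal ECG result will be summarized using descriptive statistics". SAP 7.7.5 omits it, and SAP Section 8 does not declare the change.

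Leave the within-window rule for clinic ZBPI as it is and note the limitation.

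The cost is SAP wording and a few rows or tables, with no new data. The small downside is that the end-of-treatment row mixes different exposure times, which a footnote should say.
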